## S2 students as the target population

Healthy oral behaviours should be formed at an early age. Therefore, adolescents in secondary schools are the target population. HK implemented new senior secondary curriculum (3+3) since September 2009; that three years from S1 to S3, and then three years from S4 to S6. S1 students are in a transitional period from primary school to secondary school, which requires adaptions. S3 students need to study most subjects in order to choose their discipline. S4-S6 students are at their benchmarks, and they need to make great efforts to prepare for exams. Therefore, S2 students are believed to be the most appropriate subpopulation to be enrolled in health promotion studies.

### Inclusion criteria

Inclusion criteria for participants are 1) S2 students at the baseline recruitment (September, 2018 as the start), 2) agree to voluntarily participate, and 3) do not intend to leave Hong Kong within the next 12 months since the baseline survey. Adolescents who have cognitive impairment will be excluded.

### Participants recruitment

We plan to recruit participants from secondary schools (all children are required to attend secondary school since the year 2009 by law). HK schools will be the primary sampling unit, then all S2 students in the selected schools will be recruited into this study. We will seek approval from Principle of each selected school first; then we will ask for written consents from students and their parents/caregivers. Schools that are currently receiving other oral health promotion programs will be excluded.

## (ii) Methods

## Pilot study

The questionnaire was developed by following the guideline of SCT and HBM [29-33]. A panel, consisting of a registered specialist in dentistry, a behavioural scientist, and an epidemiologist, held several meetings, and eliminated some overlapping items while combined others with similar meanings. 5 secondary school teachers, 5 dentists and 10 S2 students were invited to examine the face validity of the questionnaire. After this panel's refinement, the questionnaire was validated among our target population, 30 S2 students.

In the pilot study, the average item response rate was 93.3%, and the item mean ranged from 1.7 to 3.9, suggesting satisfactory acceptance and variance. The questionnaire took 15-20 minutes to complete. All students had a sufficient understanding of the items and found the questions not difficult to answer.

Exploratory Factor Analysis identified three factors (perceived benefits, perceived barriers and perceived severity) of HBM and two factors (self-efficacy and behavioural capability) of SCT. These factors accounted for 86.63% of the total variance. Cronbach's alpha coefficients were 0.74, 0.84, 0.86 for items of HBM and 0.96, 0.74 for items of SCT. Item-total and item-subscale correlation coefficients were also satisfactory (ranging from 0.62 to 0.94, all p<0.05).

## (iii) Study design

## Baseline survey and dental examination

The baseline survey will collect information on participants' background characteristics (e.g., socio-demographics), theory-based variables (perceived benefits, perceived barriers, perceived severity, self-efficacy and behavioural capability), and oral health behaviors. Validated scales have been identified and will be used in the survey [34, 35].

To comprehensively assess each participant's oral health status at baseline, their caries experience and periodontal condition will be recorded following the recommendations of the World Health Organization (WHO) for oral health surveys [36]. Oral hygiene status will be recorded through plaque index (PI) (Quigley Hein, 1972) on a scale of 0 to 5. Dental caries experience will be recorded by counting the numbers of permanent teeth that are decayed (DT), missing due to caries (MT), and filled (FT) to generate a DMFT score. Periodontal condition will be recorded using the Community Periodontal Index (CPI). Two trained and calibrated examiners (kappa = 0.81 - 0.87 for intra- and inter-examiner reliabilities for the assessment of DMFT and CPI) will perform the clinical examinations using a plane disposable plane intra-oral mirror with a built-in LED light source and a WHO CPI periodontal probe. Ten percent of the participants will be randomly selected and re-examined in each school to continuously monitor intra- and inter-examiner reliabilities of assessing PI DMFT and CPI.

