# c) Aims and Hypotheses to be Tested:

## Objectives

- The primary aim is to evaluate the relative efficacy of a peer-led theory-based intervention in promoting healthy oral behaviours versus the control (normal practice) on increasing the prevalence of healthy oral behaviours (tooth brushing, dental flossing, and dental visit for check-up) among adolescents in Hong Kong;
- 2) The secondary aim is to evaluate the relative efficacy of the intervention and control groups in affecting clinical oral health outcomes, including dental caries and periodontal health;
- The third aims are to evaluate the relative efficacy of the intervention and control groups in affecting secondary outcomes of thoery-based constructs including
   i) increasing paramined evaluate the intervention and control groups in
  - i) increasing perceived susceptibility towards oral diseases,
  - ii) increasing perceived severity towards oral diseases,
  - iii) increasing perceived benefits towards healthy oral behaviors,
  - iv) reducing perceived barriers of performing oral health behaviors,
  - v) provide cues to action related to oral health behaviors,
  - vi) build self-efficacy of performing oral health behaviors,
  - vii) provide social support and professional support of oral health knowledge,
  - viii) increasing outcome expecatations towards healthful oral behaviours.

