## **Hypotheses**

- The hypothesis involving clinical oral health outcomes is that a lower prevalence of dental caries and better periodontal health status will be found in the intervention group than in the control group.
- 2) The hypothesis includes that a higher prevalence of healthy oral behaviours (of any type) will be found in the intervention group than in the control group.

- 3) The hypothesis based on the third outcomes states that the intervention group as compared to the control group will have a higher score in positive theory-based constructs towards healthy oral behaviours
- d) Plan of Investigation:
  - (i) Subjects

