## Outcome indicators and potential confounders

The primary outcome is the prevalence of performing each of the three types of healthy oral health behaviors, including tooth brushing, dental flossing, and dental visit. The increase in performing healthy oral behaviors is the key of public health significance. The secondary outcome is the prevalence and severity of oral diseases, including dental caries and poor periodontal status. The third outcome is the prevalence of theory-based constructs regarding the above healthy oral behaviors, including perceived benefits, perceived barriers, perceived severity, self-efficacy and behavioural capability.

Potential confounders include socio-demographic characteristics, pre-existing oral diseases, and utilization of dental services (except for dental check-up) during the follow-up period. Such information will be collected at the baseline and follow-up survey, and between-group differences will be tested for statistical significance. Any significant differences will be adjusted in the analysis evaluating the efficacy of the intervention as compared to the control group.

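### Aim 3 promises comparisons on eight theory constructs, but only four have a named measure, and the outcome is called a prevalence where its hypothesis predicts a score

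*Protocol*

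**What the plan says.** Section c), Objectives, frames the third aim as the relative efficacy of the two arms in "affecting secondary outcomes of thoery-based constructs including" eight listed items. They are perceived susceptibility ("increasing perceived susceptibility towards oral diseases"), severity, benefits, barriers, cues to action ("provide cues to action related to oral health behaviors"), self-efficacy, support ("provide social support and professional support of oral health knowledge") and outcome expectations.

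Section d)(iii), Baseline survey and dental examination, says the survey collects "theory-based variables (perceived benefits, perceived barriers, perceived severity, self-efficacy and behavioural capability". Outcome indicators and potential confounders names the same five constructs, and the Pilot study reports the same five: "Exploratory Factor Analysis identified three factors (perceived benefits, perceived barriers and perceived severity) of HBM and two factors (self-efficacy and behavioural capability) of SCT".

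On scale, Hypotheses states that the intervention arm "will have a higher score in positive theory-based constructs towards healthy oral behaviours". Outcome indicators states: "The third outcome is the prevalence of theory-based constructs". It gives no cut-off. Section (iv), Data processing and analysis, gives one model for comparing the arms, a modified Poisson regression for binary outcomes. The t-test and Mann-Whitney test appear there only for baseline differences.

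**The concern.** Two things do not line up. First, the aim names constructs that no part of the protocol says will be measured, and one measured construct serves no aim. A construct not collected at baseline cannot be recovered later, and no analysis plan can estimate an effect on it. Perceived susceptibility and cues to action are among the health belief model components set out in the Introduction, and peer support is one of the reasons given there for expecting the programme to work. The gaps are therefore not peripheral to the theory the trial wants to test, including the planned structural equation model.

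Second, hypothesis and outcome are on different scales. A prevalence needs a threshold, and none is given. If the analysts take the outcome definition literally and use the one stated model, they would have to split each score at a point chosen later. That would discard information and leave the choice of cut-off open.

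**Working it through.** The protocol states no figure on this point to reproduce. The first check is a matching of lists.

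| Construct | In aim 3 | Named as measured (Pilot study, Baseline survey, Outcome indicators) |
|---|---|---|
| Perceived susceptibility | yes | no |
| Perceived severity | yes | yes |
| Perceived benefits | yes | yes |
| Perceived barriers | yes | yes |
| Cues to action | yes (worded as something provided) | no |
| Self-efficacy | yes | yes |
| Social/professional support | yes (worded as something provided) | no |
| Outcome expectations | yes | no |
| Behavioural capability | no | yes |

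- Aim constructs: 8. Measured constructs: 5. Overlap: 4.
- In the aim with no named measure: 8 − 4 = 4, and 4/8 = 50%.
- If cues to action and support are set aside as programme delivery: 8 − 2 = 6 aim constructs, 6 − 4 = 2 without a named measure, and 2/6 = 33%.
- Measured but in no aim: 5 − 4 = 1.

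The second check is what a split of the score would cost if the word prevalence were taken literally. This is illustrative, since no split is stated. Assumptions: a normally distributed score, a median split, a small effect and equal clusters. The cluster size of 65 and intra-cluster correlation (ICC) of 0.05 come from Sample size calculation. The protocol sets that ICC in a calculation for tooth brushing, so its use for a construct score is an assumption.

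1. Efficiency of a median split for independent students: 2/π = 0.637, a loss of 36%.
2. Design effect for the score: 1 + (65 − 1) × 0.05 = 4.20.
3. ICC after the split: (2/π) × arcsin(0.05) = 0.032. Design effect: 1 + 64 × 0.0318 = 3.04.
4. Relative efficiency in this design: 0.637 × 4.20 / 3.04 = 0.88, a loss of about 12%.

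The same steps over a range of assumed ICCs:

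| ICC of score | Design effect, score | ICC after split | Design effect, split | Relative efficiency | Loss |
|---|---|---|---|---|---|
| 0.01 | 1.64 | 0.0064 | 1.41 | 0.74 | 26% |
| 0.05 | 4.20 | 0.0318 | 3.04 | 0.88 | 12% |
| 0.10 | 7.40 | 0.0638 | 5.08 | 0.93 | 7% |

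**The case against.** The list in Outcome indicators is introduced in an open-ended way, and the questionnaire itself is not shown, so further scales could exist. This carries little weight. The list under Baseline survey is closed, although the same sentence marks background characteristics as examples only, and the pilot found the same five factors. What the text supports is that no measure is named, which is weaker than saying that none can exist.

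Cues to action and support are worded as things the programme provides, and delivery and exposure are assessed at month 6. This stands in part. The stem still lists both as outcomes on which the arms are compared, so the wording is ambiguous. Susceptibility and outcome expectations are the unambiguous gaps.

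A model for scores may be in a statistical analysis plan that is not at hand. The protocol also plans regressions on cognitions and a structural equation model. The absence of a score model is therefore not in itself a fault. But an analysis plan cannot supply data on uncollected constructs, and the protocol's own sections would still disagree with one another.

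A reader might be tempted by three stronger readings that the text does not support:

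- **That a factor analysis on 30 students caused constructs to be dropped.** The Pilot study says a panel removed overlapping items and merged similar ones before the questionnaire was validated in 30 students, and then reports the factors found. It does not say that any construct was lost through the factor analysis, or that the other four ever had items.
- **That the scores will be dichotomised at a cost of about a third of the information.** No cut-off is stated, the pilot treats the constructs as multi-item scales, and prevalence may be loose wording. The 36% figure holds only for independent students.
- **That the structural equation model would miss everything the intervention is meant to move.** Four of the eight are measured, and the protocol does not list the model's variables.

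**Conclusion.** The inconsistency is real and can be seen on the face of the protocol. The count is exact: four of eight aim constructs have a named measure, four do not, and one measured construct is in no aim. On the reading most favourable to the protocol, two of six lack a measure. The clash between a prevalence outcome and a score hypothesis is also in the current text. Whether it would lead to dichotomised scores is an inference. If it did, the loss would be about 12% under the protocol's ICC and cluster size, and 26% to 7% for ICCs from 0.01 to 0.10, given a normal score and a median split. The point does not depend on that figure. Severity is minor to moderate: the primary behaviours and the clinical outcomes are untouched, but part of a stated aim could not be reported if the survey were run as described.

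**What to change.** Make Objectives, Baseline survey and Outcome indicators name the same constructs, by one of two routes:

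- **Restrict aim 3** to severity, benefits, barriers and self-efficacy, and add behavioural capability. This is a text change at no cost, and it is the only route if baseline data have already been collected, which the protocol does not tell us.
- **Add short item sets** for susceptibility, outcome expectations and, if they are meant as outcomes, cues to action and social/professional support. This is possible only if baseline has not started. The cost is a somewhat longer survey than the 15 to 20 minutes seen in the pilot, and a check of the new items, since the existing questionnaire has already been through validation.

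If cues to action and support are meant as programme delivery, move them out of the outcome list and into the process evaluation.

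Under either route, define the third outcome as the scale score for each construct, compared between arms with adjustment for the baseline score and for clustering by school, and use that wording in both Hypotheses and Outcome indicators. Give the expected direction for each construct, since barriers are meant to fall. If a prevalence is truly wanted, fix the cut-off and the reason for it before any outcome data are seen.

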The second follow-up at months 12 will include two parts. The first part is to collect participants' self-reported data through survey, the same procedure as the first follow-up at 6 months. The 12-month follow up data suggest a prolonged impact of the intervention, as no intervention activities will be conducted between months 6 and months 12.

The second part is to do dental re-examination, using the same methods and criteria as the baseline examination. We will compare the changes of the oral health status before and after the intervention. The consistency between self-reported healthy oral health behaviors and dental examination outcomes will also be calculated. No dental examination will be conducted at 6-month follow up, as oral health status is not likely to change much within a short time period like 6 months.

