## (iv) Data processing and analysis

The intra- and inter-examiner reliabilities of assessing PI, DMFT and CPI at the tooth level will be tested through the use of the kappa statistic. Data of DMFT and CPI at the tooth level will be used to generate the oral health status at the subject level.

Intention-to-treat analysis will be conducted. Multiple imputation methods will be used [40] to deal with missing data if it occurs. Between-group (intervention versus control) baseline differences in the frequency distributions of potential confounders will be compared by using chi-square test, t-test, Mann-Whitney test or other statistics. The absolute and relative risks and number needed to treat (and 95% confidence intervals) for the binary outcomes comparing the two groups at months 6 and 12 will be derived. Comparisons between the intervention and control groups will be made for all binary outcomes, adjusting for any potential confounders showing p<.10 in the between-group baseline comparisons (if any), using modified Poisson regression with robust sandwich variance estimation. SPSS will be used for data analysis; p<.05 (2-sided) will be taken as statistically significant. The research team is very experienced in performing data analysis.

Based on the number of intervention activities that the participants are actually exposed to, we will conduct a regression analysis to explore whether the incease of numbers of activities will increase the efficacy of the intervention. Subgroup analysis will also be conducted to compare the efficacy among participants who are exposed to different (or different combinations of) intervention activities.

We will consider the variables of oral health status at baseline, and test its mediating effect on the relationship between theory-based cognitions (and changes) and healthy oral behaviors (and changes). In statistics, a mediating effect can be tested by using an interaction term, whereby the effect of an independent variable on a dependent variable varies by the level of the mediator [41]. The mediating hypothesis is supported if the regression coefficient of the interaction term onto the dependent variable is statistically significant.

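### Total DMFT cannot show that decay was treated and can be raised by the dental visits the intervention promotes; DT and FT should be compared between arms alongside it

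*Protocol*

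**What the plan says.** Under Baseline survey and dental examination, the protocol counts decayed teeth and those "missing due to caries (MT), and filled (FT) to generate a DMFT score". Under The second follow-up at months 12, this is repeated: "The second part is to do dental re-examination, using the same methods and criteria as the baseline examination". Section (iv) Data processing and analysis then states: "Data of DMFT and CPI at the tooth level will be used to generate the oral health status at the subject level". No other caries index is named.

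Outcome indicators and potential confounders puts it more generally: "The secondary outcome is the prevalence and severity of oral diseases, including dental caries and poor periodontal status". The clinical hypothesis is that "a lower prevalence of dental caries and better periodontal health status will be found in the intervention group than in the control group". Neither sentence says whether caries means DMFT above zero, DT above zero, mean DMFT or a DMFT increment. The month-12 section adds: "We will compare the changes of the oral health status before and after the intervention".

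Under Objectives, check-up visits are one of the three primary behaviours that the intervention is meant to raise. Dental service use during follow-up, other than check-ups, is listed as a potential confounder to be adjusted for if the arms differ.

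**The concern.** The index and the intervention's target pull against each other. More check-ups should mean more decay found and treated. DMFT gives no credit when decay is treated, and it rises when a dentist fills a tooth that the survey's mirror, light and probe would have passed as sound. The difference in visits between arms is one that the trial sets out to create, so this is a differential effect and not shared noise.

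At stake is the reading of the secondary caries result. Students whose decay was treated would look unchanged, and added fillings could be read as added disease, contrary to the direction of the clinical hypothesis. Using the DMFT increment does not help: a D-to-F move contributes zero to the increment, and a filling in a survey-sound tooth contributes one.

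**Working it through.** The protocol gives no effect size or power for caries, so there is no stated figure to reproduce. The check has one step that needs no assumed rate and two that do.

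**1. The index itself.** DMFT = DT + MT + FT. A student with D=2, M=0, F=0 whose two teeth are filled becomes D=0, M=0, F=2. DMFT goes from 2 to 2, DT from 2 to 0 and FT from 0 to 2. Extracting a decayed tooth because of caries also leaves DMFT unchanged. Filling a tooth that would still be scored sound at month 12 adds 1.

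**2. Mean DMFT (all rates assumed).** Extra check-up attendance in the intervention arm is taken as 5 to 16 points. The upper end borrows the brushing target (20% of 80% = 16 points), since the protocol states no target for check-ups.
- Artefact, if 10% to 30% of extra attenders get one filling in a survey-sound tooth: 0.05 × 0.10 = 0.005 to 0.16 × 0.30 = 0.048 per student.
- Preventive effect, with a yearly increment of 0.2 to 0.3 and 15% to 20% prevention: 0.2 × 0.15 = 0.03 to 0.3 × 0.20 = 0.06 per student.
- Ratio: 0.005 / 0.06 = 8% to 0.048 / 0.03 = 160%.
- Fall in mean DT from treatment alone, if 30% to 50% of extra attenders have one decayed tooth filled: 0.05 × 0.30 = 0.015 to 0.16 × 0.50 = 0.08. DMFT changes by 0.

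**3. Prevalence of DMFT above zero.** The introduction reports that fewer than 40% of those aged 13 to 18 were caries free. I take 60% as already positive at baseline; apart from scoring error they cannot revert. Let *i* be the 12-month incidence among the caries-free, RR = 0.7 (assumed 30% prevention), and *r* the share of caries-free intervention students given a filling in a survey-sound tooth.

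Control = 0.60 + 0.40 × *i*. Intervention = 0.60 + 0.40 × [1 − (1 − 0.7*i*)(1 − *r*)].

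Example with *i* = 10% and *r* = 3%: control 0.640; intervention 0.60 + 0.40 × (1 − 0.93 × 0.97) = 0.639.

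Difference, intervention minus control, in percentage points:

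| Incidence *i* | *r* = 0 | *r* = 3% | *r* = 5% |
|---|---|---|---|
| 5% | −0.6 | +0.6 | +1.3 |
| 10% | −1.2 | −0.1 | +0.7 |
| 20% | −2.4 | −1.4 | −0.7 |

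With no preventive effect (RR = 1), *r* of 1% to 5% gives +0.3 to +1.9 points, an apparent harm with no new disease. Depending on the assumptions, a true benefit survives, vanishes or changes sign.

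**The case against.** The strongest reply is that the protocol never commits to total DMFT as the caries outcome. The outcome and hypothesis sentences speak of caries in general, DT, MT and FT are counted separately, and tooth-level DMFT data are decayed, missing and filled codes from which DT can be derived. A statistical analysis plan, which was not available here, could specify a component analysis. This stands, and it limits the point to what the protocol names: DMFT is the only caries index given, and nothing in the text acknowledges that visits shift its components.

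Second, half the mechanism is simply DMFT being cumulative. Only fillings in survey-sound teeth are an added artefact, and only if those teeth would still be scored sound at month 12; otherwise they would have counted as D anyway. This also stands.

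Third, a reader might infer that extra visits can never improve the DMFT comparison, or that success on check-ups must hide or reverse the caries result. The documents do not support either. Restorative care cannot lower a person's DMFT, but preventive care or advice at visits, and better brushing and flossing, can lower the 12-month increment relative to control. Reversal depends on rates that the protocol does not give, and the table shows benefit surviving at 20% incidence.

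Fourth, a reader might infer that DT should replace DMFT. DT has its own visit artefact in the favourable direction: treatment alone could lower it by 0.015 to 0.08, against an assumed preventive effect of 0.03 to 0.06. Fillings could then pass as prevention. This objection is correct, and the fix is built around it.

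Finally, the protocol does record dental service use during follow-up. Adjusting for it is no remedy: it is measured after randomisation and may itself result from the intervention.

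**Conclusion.** The point holds in a conditional form. That total DMFT and its increment cannot show treated decay follows from the definition of the index. That extra visits can raise DMFT in the intervention arm is a real mechanism of unknown size. The 8% to 160% range rests wholly on assumed attendance, filling, incidence and prevention rates, and it is too wide to say that harm is likely. It shows only that a DMFT-only comparison can mask, and under some rates reverse, a caries benefit. This concerns a secondary outcome; it is an inexpensive improvement and does not threaten the primary comparison.

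**What to change.** In Outcome indicators and potential confounders, and in section (iv) Data processing and analysis:

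- Keep the DMFT comparison, as the month-12 value or the increment, adjusted for baseline DMFT.
- Alongside it, compare DT (any, and number of teeth) and FT between arms at month 12, each adjusted for its own baseline value.
- State the reading in advance: a fall in DT matched by a rise in FT is care received, not prevention; a rise in FT alone is not read as more disease.
- Do not make DT the sole or main caries outcome.
- Do not rely on adjustment for dental service use during follow-up to deal with this.

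The cost is a few sentences and two extra reported measures. No new data are needed, since the components are counted at both examinations. The remaining drawback is that DT taken alone is lowered by treatment, so it must always be shown with FT and DMFT.
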